5. SAMPLE SIZE CONSIDERATIONS

This study is planned to enroll a minimum of 60 subjects in Groups 1-2, and 30 subjects in Group 3. This study is not designed to test a formal null hypothesis. Rather, it is intended to obtain sufficient data to obtain meaningful estimates of the immune response and to uncover any safety issues that occur at a sufficiently high rate that they might be observed in a study of this size. As such, the type one error rate, $\alpha = 0.05$, is not adjusted for multiple comparisons. While this study is not designed to test any specific null hypothesis, the following tables illustrate the precision and power that is available for select estimates and comparisons of interest.

[Table 8](#) indicates the probability of observing one or more safety events, such as solicited injection site or systemic reactogenicity events or an unsolicited non-serious AE of a particular type for a single treatment group ($N = 30$ or 60), and for all subjects receiving AS03-adjuvanted 2017 H7N9 IIV ($N = 120$).

Binomial confidence intervals (CI) are widest (have the least precision) when the response rate is 50%. [Table 9](#) is presented to indicate the worst case scenario for precision of observed exact (Clopper-Pearson) binomial confidence intervals.

For each of the primary immunogenicity objective, a power analysis is provided below for testing the following hypotheses with the planned sample size, where p_c = proportion responders in comparator arm; p_e = proportion responders in experimental arm.

Test for difference in proportion responders:

$H_0: p_c - p_e = 0$ – No difference in proportion responders

$H_1: p_c - p_e \neq 0$ – difference in response rates

Primary Immunogenicity Objective 1: Evaluate antibody responses against A/H7N9 at approximately 21 days following receipt of two doses of AS03-adjuvanted 2017 H7N9 IIV. Comparison between simultaneous and sequential receipt to IIV4, i.e., Group 1 at Day 43 vs. Group 2 at Day 64.

Primary Immunogenicity Objective 2: Evaluate antibody responses against the seasonal influenza strains at approximately 21 days following receipt of IIV4.

Comparator Group ($N = 75$):

- Group 2 (IIV4/H7N9/H7N9) + Group 3 (IIV4) at Day 22

Experimental Groups ($N = 50$ /group):

- Group 1 (IIV4+H7N9 /H7N9) at Day 64

[Table 10](#) and [Table 11](#) illustrate the minimum detectable differences in the proportion of subjects responding (e.g., attaining seroconversion or a titer $\geq 1:40$) between two treatment groups using a two-sided Likelihood Ratio Test and $\alpha = 0.05$.

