11.4.2 Subject Enrollment and Follow-up

Based on the accrual rates observed in similar studies, it seems reasonable to expect that the participating VTEUs will be able to enroll this trial in a timely fashion. In previous DMID trials of A/H7N9 vaccines, 5 VTEUs recruited 975 healthy adults, ages 19-64 in 10 weeks. Prior experience suggests up to 15% of subjects may be excluded from the per protocol analysis for post dose 3 assessments, either because they did not receive the second or third study vaccinations, were lost-to-follow-up, or because they had a protocol deviation requiring their exclusion from the per protocol analysis.

A total of N=60 in Groups 1-2, and N = 30 in Group 3 will be enrolled and randomized. Assuming up to 15% drop out by Day 64, this will ensure at least N=50 in Groups 1-2 and N=25 in Group 3 are available for the primary immunogenicity analysis.

Follow-up will consist of 2 segments. The first encompasses the core data for this trial and will consist of results for all study visits through approximately 21 days after the last study vaccination. The second segment consists of a 6-month immunogenicity assessment and follow-up safety assessments through approximately 12 months after the last study vaccination.

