3.2. Endpoints

3.2.1. Primary

Safety:

- Occurrence of all serious adverse events (SAEs) following the first study vaccination through approximately 12 months after the last study vaccination.
- Occurrence of study vaccine-related SAEs following the first study vaccination through approximately 12 months after the last study vaccination.
- Occurrence of solicited injection site and systemic adverse events (AEs) following each study vaccination through 7 days after each study vaccination.
- Occurrence of clinical safety laboratory AEs following each study vaccination through approximately 7 days after each study vaccination.

Immunogenicity:

- For HAI and Neut antibodies, percentage of subjects achieving seroconversion against the 2017 H7N9 study vaccine strain (defined as either a pre-vaccination titer <1:10 and a post-vaccination titer \geq 1:40 or a pre-vaccination titer \geq 1:10 and a minimum four-fold rise in post-vaccination antibody titer) at approximately 21 days after 2 doses of AS03-adjuvanted 2017 H7N9 IIV (Group 1 – Day 43; Group 2 – Day 64; Group 3 – N/A).
- For HAI and Neut antibodies, percentage of subjects achieving seroconversion against each of the study IIV4 strains at approximately 21 days after receipt of study IIV4 (Groups 1, 2 and 3 – Day 22).
- For HAI and Neut antibodies, percentage of subjects with an antibody titer of \geq 1:40 against the influenza 2017 H7N9 study vaccine strain at approximately 21 days following receipt of 2 doses of AS03-adjuvanted 2017 H7N9 IIV (Group 1 – Day 43; Groups 2 – Day 64; Group 3 – N/A).
- For HAI and Neut antibodies, percentage of subjects with an antibody titer of \geq 1:40 against each of the study IIV4 strains at approximately 21 days after receipt of study IIV4 (Groups 1, 2 and 3 – Day 22).

- GMTs of serum HAI and Neut antibodies against the 2017 H7N9 IIV strain at approximately 21 days following receipt of 2 doses of AS03-adjuvanted 2017 H7N9 IIV (Group 1– Day 43; Group 2 – Day 64; Group 3 – N/A).
- GMTs of serum HAI and Neut antibodies against each of the 2017 IIV4 strains at approximately 21 days after receipt of IIV4 (Group 1, 2 and 3– Day 22).

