6.3.2. Modified Intention-to-Treat (mITT) Population

The modified intent-to-treat (mITT) population includes all subjects who received at least one dose of study vaccine and contributed both pre- and at least one post-study vaccination venous blood samples for immunogenicity testing (HAI or Neut antibody assays) for which valid results were reported. For analyses using the mITT population, subjects in Group 2 who discontinue treatment after receiving the single IIV4 dose (Dose 1) but prior to receiving the first dose of the H7N9 vaccine (Dose 2) will be analyzed with group 3. All other subjects will be grouped based on randomized treatment group.

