8.1. Primary Immunogenicity Analysis

The primary immunogenicity endpoints HAI and Neut seroconversion, percentage of subjects with titer $\geq 1:40$, and GMTs against the seasonal IIV4 strains 21 days after the IIV4 vaccination for all groups and against the homologous A/H7N9 vaccine strain 21 days after the second dose of AS03 adjuvanted 2017 H7N9 IIV will be summarized as described above. The primary analysis population will be mITT, with results from the PP population providing a comparison of the sensitivity of immunogenicity results to subject adherence to protocol-

defined conditions. Regression modelling of seroconversion and log titers is planned as described in Section 8.3.2.

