8.3.2. Regression Modeling

Logistic and multivariate linear regression will be utilized to test for the effects of the treatment schedule on seroconversion and GMT against the homologous 2017 A/H7N9 strain and against each of the seasonal IIV4 strains for the PP population. Similar models will be fit for HAI and Neut Antibodies for each strain and time point. Separate models will be fit for data from Day 21 post dose and Day 180 post dose.

Logistic regression will be fit to examine the relationship of HAI or Neut seroconversion at 21 or 180 days after the dose of interest (second dose of AS03 adjuvanted A/H7N9 IIV for the 2017 A/H7N9 strain; IIV4 vaccination for the seasonal IIV4 strains) with treatment schedule. If the available titer data meets the required assumptions of normality after log

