N = XX (Number of subjects in the Per Protocol Population)
n = XX (number of subjects with results available at 21 days post second dose of AS03 adjuvanted A/H7N9 IIV in the per protocol population).
XX subjects missing covariate data were excluded from this analysis.

Tables with similar format:

Table 69: Logistic Regression Model to Evaluate the Relationship of Administration Schedule with HAI Seroconversion Against 2017 A/H7N9 at 180 Days Post Second Dose of AS03 adjuvanted A/H7N9 Vaccine, Per Protocol Population *

Table 70: Logistic Regression Model to Evaluate the Relationship of Administration Schedule with Neut Seroconversion Against 2017 A/H7N9 at 21 Days Post Second Dose of AS03 adjuvanted A/H7N9 Vaccine, Per Protocol Population

Table 71: Logistic Regression Model to Evaluate the Relationship of Administration Schedule with Neut Seroconversion Against 2017 A/H7N9 at 180 Days Post Second Dose of AS03 adjuvanted A/H7N9 Vaccine, Per Protocol Population

Table 72: Logistic Regression Model to Evaluate the Relationship of Administration Schedule with HAI Seroconversion Against Seasonal IIV4 Strains at 21 Days post IIV4 Vaccination, Per Protocol Population*

Model Parameter	Parameter Category	Parameter Estimate	SE	p-value	Odds Ratio	95%CI
A/Michigan/45/2015 X-275 (H1N1)						
Intercept	N/A	xxx.x	xxx.x	x.xxx	-	-
Treatment	Simultaneous Administration (reference)	-	-	-	-	-
	Sequential Administration	xxx.x	xxx.x	x.xxx	xx.x	xx.x-xx.x
	IIV4 Only	xxx.x	xxx.x	x.xxx	xx.x	xx.x-xx.x
[Repeat for all IIV4 Strains]						
N = XX (Number of subjects in the Per Protocol Population) n = XX (number of subjects with results available at 21 days post IIV4 vaccination in the per protocol population). XX subjects missing covariate data were excluded from this analysis.						

Tables with similar format:

Table 73: Logistic Regression Model to Evaluate the Relationship of Administration Schedule with HAI Seroconversion Against Seasonal IIV4 Strains at 180 Days Post IIV4 Vaccination, Per Protocol Population

Table 74: Logistic Regression Model to Evaluate the Relationship of Administration Schedule with Neut Seroconversion Against Seasonal IIV4 Strains at 21 Days Post IIV4 Vaccination, Per Protocol Population*

Table 75: Logistic Regression Model to Evaluate the Relationship of Administration Schedule with Neut Seroconversion Against Seasonal IIV4 Strains at 180 Days Post IIV4 Vaccination, Per Protocol Population

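### Power for the seasonal-vaccine objective is tabulated for Group 1 against Groups 2 and 3 pooled, but every planned 21-day model compares Group 1 with each of them separately

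*SAP*

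**What the plan says.** Protocol 11.4.3 and SAP 5 define the Objective 2 comparator as "Group 2 (IIV4/H7N9/H7N9) + Group 3 (IIV4) at Day 22" (N = 75) and the experimental arm as Group 1 (N = 50). Protocol Table 6 and SAP Table 11 then give minimum detectable decreases at 80% power. SAP 5 introduces these tables by saying that "the following tables illustrate the precision and power that is available for select estimates and comparisons of interest". The group sizes come from Protocol 11.4.2: "Assuming up to 15% drop out by Day 64, this will ensure at least N=50 in Groups 1-2 and N=25 in Group 3".

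On the analysis side, SAP 8.1 has the primary endpoints summarized by group and adds: "Regression modelling of seroconversion and log titers is planned as described in Section 8.3.2". Section 8.3.2 says: "Logistic and multivariate linear regression will be utilized to test for the effects of the treatment schedule on seroconversion and GMT". The shell for "HAI Seroconversion Against Seasonal IIV4 Strains at 21 Days post IIV4 Vaccination" (Table 72) lists Simultaneous Administration as reference, with one row for Sequential Administration and another for IIV4 Only, each with its own estimate and p-value. Tables 80, 88 and 96 have the same layout, and Tables 74, 82, 90 and 98 follow in similar format. SAP 6.1 gives the summary tables one column per group.

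The only merging of Groups 2 and 3 is in the population definitions (SAP 6.3.2 and 6.3.3): Group 2 subjects who stop after IIV4 "but prior to receiving the first dose of the H7N9 vaccine (Dose 2) will be analyzed with group 3".

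**The concern.** Whether co-administration weakens the seasonal response is one of the two interference questions named in Protocol 11.1. The detectable differences offered for it belong to a comparison that no table, model or contrast will report. The contrasts that will be reported are less precise, markedly so against the 30-subject IIV4-only arm. Each strain and assay also gets two answers, Group 1 versus 2 and Group 1 versus 3, with no rule for which one addresses Objective 2 if they differ.

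The merging rule adds a complication. It moves some Group 2 subjects into Group 3 after randomization, which alters both separate contrasts but leaves a pooled comparison unchanged.

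Objective 1 does not have this problem: Table 5/10 (50 vs 50) matches the two-level model in SAP Table 68.

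**Working it through.** **Inputs.** Two-sided likelihood ratio test, alpha 0.05 (Protocol 11.4.3, SAP 5). Comparator response p_c = 0.40 to 0.90 with decreases d = 0.23, 0.24, 0.25, 0.25, 0.23, 0.20 (Table 6/11). Allocation 2:2:1, i.e. 60/60/30 enrolled. The plan's 15% loss leaves 60 × 0.85 = 51 and 30 × 0.85 = 25.5, used as 50/50/25.

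**Method.** For responder counts x_c and x_e, G = 2 × (log-likelihood with separate proportions − log-likelihood with a common proportion). Reject when G exceeds the 5% critical value of chi-square with 1 df. Power is the sum of Bin(x_c; n_c, p_c) × Bin(x_e; n_e, p_c − d) over all rejecting pairs, by full enumeration. An unadjusted three-level logistic model gives each contrast the same estimate as the matching two-group comparison, so two-group power is the right yardstick.

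**Step 1: reproduce the plan.** At 75 vs 50, the 80% detectable decreases are 0.228, 0.244, 0.251, 0.250, 0.234, 0.196. These agree with all six stated values. The same method at 50 vs 50 gives 0.266, 0.271, 0.270, 0.260, 0.221 for p_c 0.5 to 0.9, which agrees with Table 5/10.

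**Step 2: power at the Table 6/11 differences** (comparator n / Group 1 n)

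| p_c | d | Pooled 75/50 | vs Group 2, 50/50 | vs Group 3, 25/50 |
|---|---|---|---|---|
| 0.40 | 0.23 | 0.811 | 0.737 | 0.568 |
| 0.50 | 0.24 | 0.788 | 0.708 | 0.543 |
| 0.60 | 0.25 | 0.798 | 0.734 | 0.571 |
| 0.70 | 0.25 | 0.801 | 0.737 | 0.575 |
| 0.80 | 0.23 | 0.791 | 0.707 | 0.539 |
| 0.90 | 0.20 | 0.816 | 0.735 | 0.561 |

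**Step 3: sensitivity to loss.** The 15% is stated for Day 64. Loss by Day 22 is not stated, so a range is shown.

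| Loss by Day 22 | Pooled | vs Group 2 | vs Group 3 |
|---|---|---|---|
| As planned (50/50/25) | 79–82% | 71–74% | 54–58% |
| 5%, assumed (57/57/28) | not computed | 76–79% | 58–62% |
| None, assumed (60/60/30) | 86–88% | 78–82% | 61–66% |

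**Step 4: 80% detectable decreases for the reported contrasts** (p_c 0.4 to 0.9)

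- 50 vs 50: 0.246, 0.266, 0.271, 0.270, 0.260, 0.221.
- 50 vs 25: 0.288, 0.316, 0.328, 0.326, 0.318, 0.277.

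**Step 5: log titer.** With a common variance, the standard error of a contrast is proportional to √(1/n₁ + 1/n₂).

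- Group 2 versus pooled comparator: √(1/50 + 1/50) / √(1/50 + 1/75) = 0.2000 / 0.1826 = 1.10.
- Group 3 versus pooled comparator: √(1/50 + 1/25) / 0.1826 = 0.2449 / 0.1826 = 1.34.

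Both ratios are the same at 60/60/30.

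**Step 6: is pooling valid at Day 22?** Groups 2 and 3 have each received only IIV4 by then, and Group 2's Day 22 blood is drawn immediately before its first H7N9 dose (Protocol 8.3.3). At Day 180 this no longer holds, because Group 2 has also had H7N9.

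**Step 7: the time point.** Protocol 11.4.3 and SAP 5 place Group 1 at Day 64 under Objective 2. The endpoint in SAP 3.2.1 is "approximately 21 days after receipt of study IIV4 (Groups 1, 2 and 3 – Day 22", and Group 1's Day 64 visit draws serum for future research only (Protocol 8.2.7, Table 2a). The endpoint text governs, and the slip does not affect the detectable differences.

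**The case against.** The strongest reply is about weight. Both documents say that no formal null hypothesis is tested and that the power tables are illustrative. The primary analysis is a set of per-group summaries with confidence intervals in the mITT population. The regressions sit under the exploratory heading (SAP 8.3) and use the PP population, and Protocol 11.6.3 says only that such models may be developed. Table 4/9 already gives per-arm precision at N = 30 and 60, and Table 5/10 covers 50 vs 50 for p_c 0.5 to 0.9. If little is lost by Day 22, Group 1 versus Group 2 has close to 80% power anyway. A reader could approximate the pooled result from the by-group figures in SAP Tables 32–35. Adding a contrast touches eight tables of four strains, so 32 more p-values beside 64, with no multiplicity adjustment.

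Most of this stands as a limit on severity. The large shortfall is confined to the Group 3 contrast, and the number of Group 2 subjects likely to be moved into Group 3 is not given, so that effect cannot be sized. It does not remove the mismatch. SAP 8.1 invokes these models in the primary immunogenicity section, the shells report p-values, and SAP 5 writes out null and alternative hypotheses and offers a power analysis for each primary immunogenicity objective. An illustrative figure should still describe a comparison that will be reported. Naming one contrast in advance as the Objective 2 answer reduces selective reading rather than adding to it.

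**Conclusion.** The concern holds. Table 6/11 is arithmetically right for 75 vs 50 but describes no planned analysis. At its stated differences, the reported contrasts have 71–74% power against Group 2 and 54–58% against Group 3 under the plan's own loss allowance, rising to 78–82% and 61–66% with no loss. The 80% detectable decreases widen from 0.20–0.25 to 0.22–0.27 and 0.28–0.33.

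These figures assume unadjusted comparisons and the likelihood ratio test named in the plan; the regression p-values may be Wald-based. The separate contrasts are valid, only less precise. This should be fixed, but it does not undermine the planned by-group summaries.

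**What to change.** - **Preferred.** In SAP 8.3.2 and the eight 21-day seasonal-strain shells, pre-specify Group 1 versus Groups 2+3 combined as the Objective 2 contrast, and label the separate contrasts supportive. A two-level treatment variable matches the tabulated comparison directly. Keep three levels at Day 180.
- **If pooling is declined.** Restate Table 6/11 for p_c 0.4 to 0.9 with the contrasts that will be reported: 0.25, 0.27, 0.27, 0.27, 0.26, 0.22 for 50 vs 50, and 0.29, 0.32, 0.33, 0.33, 0.32, 0.28 for 50 vs 25. Say which contrast answers Objective 2.
- **Either way.** Change Group 1's time point under Objective 2 from Day 64 to Day 22 in Protocol 11.4.3 and SAP 5.

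The cost is SAP wording, one added contrast per model (32 models) or one revised table, and a small correction in each document. No extra participants or samples are needed.

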6. GENERAL STATISTICAL CONSIDERATIONS

6.1. General Principles

All continuous variables will be summarized using the following descriptive statistics: n (non-missing sample size), mean, standard deviation, median, maximum and minimum. The frequency and percentages (based on the non-missing sample size) of observed levels will be reported for all categorical measures. In general, all data will be listed, sorted by site, treatment and subject, and when appropriate by visit number within subject. All summary tables will be structured with a column for each treatment group in the following order:

- Group 1: Simultaneous Administration (D1: IIV4/H7N9; D22: H7N9)
- Group 2: Sequential Administration (D1: IIV4; D22: H7N9; D43: H7N9)
- Group 3: IIV4 Only (D1: IIV4)

All tables will be annotated with the total population size relevant to that table/treatment, including any missing observations.

6.2. Timing of Analyses

6.2.1. Preliminary Report and CSR

Clinical, safety, and reactogenicity data through Day 64 will represent the primary clinical database for this trial. Once the last subject completes the Day 64 visit, the primary clinical database will be cleaned, monitored, and locked. Analyses of safety, reactogenicity, and available immunogenicity (HAI and Neut antibody assays through day 64) data by treatment arm are planned. A preliminary report will be prepared by the SDCC after the primary clinical database is locked and all HAI and Neut data through 21 days after the last study vaccination are received. Immunogenicity and safety analyses will be presented in aggregate by treatment group; individual subject data will not be presented in the preliminary report. These analyses may be made available to the sponsor for planning subsequent trials and to the lead principal investigator for publication. These analyses will not be used to make any decisions concerning the conduct of this trial. All analyses of data included in the preliminary report for early release will be considered the final analysis of these data, and also included in the final CSR.

Tables and figures to be included in the Preliminary Report are indicated with the symbol * in the title.

Analysis of exploratory immunogenicity endpoints may be performed and released as the data are available from the research laboratory. Any such analyses would be considered the final analysis for the endpoint, and included in the CSR.

The final CSR will be completed after the last subject's last visit is completed, and the final clinical database including all long-term safety follow-up data is cleaned, monitored and

locked. Additional exploratory immunogenicity endpoint data not available at the time of CSR preparation may be included in an addendum to the CSR.

6.3. Analysis Populations

6.3.1. Safety Population

The Safety Analysis population includes all subjects who received at least one study vaccination.

6.3.2. Modified Intention-to-Treat (mITT) Population

The modified intent-to-treat (mITT) population includes all subjects who received at least one dose of study vaccine and contributed both pre- and at least one post-study vaccination venous blood samples for immunogenicity testing (HAI or Neut antibody assays) for which valid results were reported. For analyses using the mITT population, subjects in Group 2 who discontinue treatment after receiving the single IIV4 dose (Dose 1) but prior to receiving the first dose of the H7N9 vaccine (Dose 2) will be analyzed with group 3. All other subjects will be grouped based on randomized treatment group.

6.3.3. Per Protocol Population

The per protocol (PP) population includes all subjects in the mITT subset with the following exclusions:

- Data from all available visits for subjects found to be ineligible at baseline.
- Data from all visits subsequent to major protocol deviations, such as:
 - Second or third dose not received,
 - Second or third dose received out of window,
 - Receipt of non-study licensed live vaccine within 30 days before or after each study vaccination,
 - Receipt of non-study licensed inactivated vaccine within 14 days before or after each study vaccination,
 - Receipt of immunosuppressive therapy (e.g., corticosteroids) within 30 days before or after each study vaccination.
- Data from any visit that occurs out of window by more than one day.

For analyses using the PP population, subjects will be grouped based on study vaccinations received - subjects in Group 2 who discontinue treatment after receiving the single IIV4 dose (Dose 1) but prior to receiving the first dose of the H7N9 vaccine (Dose 2) will be analyzed with Group 3.

